1. LIST OF ABBREVIATIONS AND ACRONYMS

AE	adverse event
ALT	alanine aminotransferase
AST	aspartate aminotransferase
CV	coefficient of variation
DPV	dapivirine
eCRF	electronic case report form
HIV	Human Immunodeficiency Virus
HIV-1	Human Immunodeficiency Virus type 1
PD	pharmacodynamics
PK	pharmacokinetics
SAP	statistical analysis plan
SGOT	serum glutamic-oxaloacetic transaminase
SGPT	serum glutamic pyruvic transaminase
SMC	study monitoring committee
STI	sexually transmitted infection
$t_{1/2}$	terminal elimination half-life

2. INTRODUCTION

The purpose of this Statistical Analysis Plan (SAP) is to provide a description of the statistical analyses that will be conducted to assess the safety, pharmacokinetics and acceptability of the dapivirine gel administered into the rectum, when compared to a placebo gel, among HIV-uninfected men and women.

2.1 General Design Considerations

The following is a protocol summary of the study.

Protocol title:	A Randomized, Double Blind, Placebo-Controlled Phase 1 Safety and Pharmacokinetic Study of the Dapivirine Gel (0.05%) Administered Rectally to HIV-1 Seronegative Adults
Short Title:	Dapivirine Gel Rectal Safety and PK Study
Clinical Phase:	Phase 1
IND Sponsor:	DAIDS
Protocol Chair:	[name], FRCP
Sample Size:	approximately 27 participants
Study Population:	HIV-uninfected men and women between the ages of 18 and 45 years (inclusive)
Study Sites:	Sites selected by the MTN leadership
Study Design:	Phase 1, two-arm, placebo-controlled, double-blinded, multi-site, randomized trial (2:1)
Study Duration:	Approximately 40 days of follow-up per participant is planned with a projected accrual period of 6-8 months
Study Products:	Dapivirine gel (0.05%)

Study Regimen: Universal HEC placebo gel
Participants will be randomized in a 2:1 ratio to receive a single dose of either dapivirine gel or universal HEC placebo gel rectally, followed by 7 daily doses of the same product to be administered under direct observation in the clinic.

2.2 Study Objectives and Endpoints

Primary Objectives:

Safety

- To assess the safety of dapivirine gel formulation when applied rectally.

Pharmacokinetics

- To characterize the systemic and compartmental pharmacokinetics of dapivirine gel following rectal application.

Secondary Objectives:

Acceptability

- To identify product attributes considered likely to challenge and facilitate future sustained use of rectally applied dapivirine gel.

Mucosal Safety

- To evaluate the mucosal safety of dapivirine gel when applied rectally.

Exploratory Objectives:

Ex Vivo Efficacy

- To assess the preliminary (ex vivo) efficacy of dapivirine gel formulation after product is applied rectally.

Pharmacokinetics

- To characterize the vaginal pharmacokinetics of dapivirine gel following rectal application in women.

Primary Endpoints:

Safety

- The proportion of participants with:
 - Grade 2 or higher AEs as defined by the Division of AIDS Table for Grading the Severity of Adult and Pediatric Adverse Events, Corrected Version 2.1, July 2017 and/or Addenda 1, 2 and 3 (Female Genital [Dated November 2007], Male Genital [Dated November 2007] and Rectal [Clarification Dated May 2012] Grading Tables for Use in Microbicide Studies).

Pharmacokinetics

- Dapivirine concentrations
 - Blood
 - Rectal fluid
 - Rectal mucosal tissue homogenates.

Secondary Endpoints:

Acceptability

- Product attributes considered likely challenge future sustained use

Mucosal Safety

- Rectal Proteomics
- Rectal transcriptome
- Rectal microflora
- Rectal histology
- Rectal tissue flow cytometry

Exploratory Endpoints:

Ex Vivo Efficacy

- Changes in HIV-1 p24 levels in colorectal explant culture supernatant
- Anti-HIV activity in rectal fluid
- Anti-HIV activity in cervicovaginal fluid (in women)

Pharmacokinetics

- Dapivirine concentrations
 - Cervicovaginal fluid (in women)
 - Cervical tissue (in women)

2.3.1 Randomization

Participants were randomized in a 2:1 ratio to the dapivirine and placebo arms, stratified by study site.

Participants were also sequentially assigned in a 1:1 ratio to provide intensive PK samples at either 30-60 or 120 minutes after administration of the gel on Visits 3 and 13. Participants were also sequentially assigned in a 1:1:1 ratio to provide intensive PK samples at either Visits 4 and 14, Visits 5 and 15 or Visits 6 and 16.

The randomization scheme has been generated and maintained by the MTN SDMC.

2.3.2 Blinding

Study staff and participants are blinded to the random treatment assignment of all study participants.

2.3.3 Sample Size and Power

The proposed sample size for this study was 27 participants, with 18 in the active arm and 9 in the control arm. The study has power to detect only very large differences in safety event rates between active and control arms. With 5% significance level, the study has 85% power to detect a rate in safety endpoint greater than 67% in the active arm when assuming an 11.2% rate in the control arm. On the other hand, the proposed sample size ensures a reasonable frequency of safety events that are not too rare. For example, if the true event rate of an adverse event is 10%, then the probability of observing at least one adverse event in the study is 85%.

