5. GENERAL ANALYSIS METHODS

Descriptive statistics will be used to summarize continuous (mean and standard deviation, median and interquartile range, quartiles, range, and number of missing data values) and categorical (frequencies, relative frequencies, percentages, and number of missing data values) outcomes. Line, scatter, and box plots will be used, as appropriate, to visualize trends in longitudinally repeated measures.

Confidence intervals will be obtained using the Clopper-Pearson method for binary outcomes, while for continuous outcomes these will be based on the Student's-*t* statistic. Unless otherwise specified, 95% confidence intervals will be provided.

When use of formal testing to assess differences between participants in active and placebo arms are required, the following methods will be used: for binomial response variables, a Fisher's exact test; for continuous variables, t-tests or nonparametric methods. Unless otherwise specified, results from two-sided hypothesis tests will be reported.

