8. PRIMARY ENDPOINT ANALYSES

8.1 Adverse Events

For the analysis of the primary safety endpoint, we will present the number and the proportion of participants experiencing at least one Grade 2 or higher adverse event, overall and by study arm. Each participant will contribute once in each category (i.e., only the highest severity AE of each participant) for the calculation of event risks. Exact binomial confidence intervals, using the Pearson-Clopper method, will be provided and Fisher's Exact test will be used to test for differences in risks between the arms.

Additionally, we will also present the following listings and tables of Adverse Events. No formal statistical testing will be conducted.

- The total number (and percentage) of adverse experiences by severity and relationship to study product, overall and for each study arm and for each site.
- Number and percentages of adverse experiences by body system/MedDRA preferred term and severity, by study arm and by site.
- Number and percentages of adverse experiences by body system/MedDRA preferred term and relationship to study product, by study arm and by site.
- Cumulative listing of Adverse Events, with arm, site and participant ID, MedDRA preferred term and AE verbatim, severity, relationship to study product, date reported to site, onset date, outcome date, duration in days, treatment, and outcome.

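### The 85% power in SAP section 2.3.3 is not that of the planned Fisher's exact test, which has 82.5% at 67% versus 11.2% with 18 and 9 participants

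*SAP*

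**What the plan says.** Section 2.3.3 (Sample Size and Power) sets the size at 27 participants, "with 18 in the active arm and 9 in the control arm". It then makes its one statement about between-arm power: "the study has 85% power to detect a rate in safety endpoint greater than 67% in the active arm when assuming an 11.2% rate". The 11.2% is the assumed control-arm rate, and the level is given as 5%. The section names neither the test nor its sidedness.

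Both are fixed elsewhere in the SAP. Section 8.1 (Adverse Events) says that, for the proportion of participants with a Grade 2 or higher event, Fisher's "Exact test will be used to test for differences in risks between the arms". Section 5 (General Analysis Methods) also assigns Fisher's exact test to binomial responses and adds: "Unless otherwise specified, results from two-sided hypothesis tests will be reported".

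**The concern.** A power figure describes a particular test. Here the test is fixed as a two-sided Fisher's exact test at 5% with arms of 18 and 9. At that size Fisher's test is conservative, so a power computed from a large-sample approximation will usually be too high. A reader who applies the SAP's own test to the SAP's own rates should obtain 85%. If not, the detectable rate is understated and the only comparative power claim is optimistic.

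**Working it through.** **Inputs.** Active arm n = 18, control arm n = 9, active rate 0.67, control rate 0.112 and level 0.05 come from section 2.3.3. The test comes from sections 5 and 8.1, and two-sidedness from section 5.

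**Step 1: reproduce the 85%.** Use the pooled normal approximation without continuity correction.

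- Pooled rate: (18 × 0.67 + 9 × 0.112)/27 = 0.484.
- SE under the null: √[0.484 × 0.516 × (1/18 + 1/9)] = 0.2040.
- SE under the alternative: √[0.67 × 0.33/18 + 0.112 × 0.888/9] = 0.1528.
- Power: Φ[(0.558 − 1.960 × 0.2040)/0.1528] = Φ(1.035) = 0.8497.

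The stated 85% is reproduced. The exact power of the uncorrected chi-square test, from the same enumeration as in step 2, is 85.4%.

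**Step 2: power of the planned test.** Let X ~ Bin(18, 0.67) be the active count and Y ~ Bin(9, 0.112) the control count. For each control count y, find the smallest active count k at which the two-sided Fisher p-value is at most 0.05, then sum P(Y = y) × P(X ≥ k).

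| y (of 9) | P(Y = y) | k (of 18) | P(X ≥ k) | Product |
|---|---|---|---|---|
| 0 | 0.3433 | 8 | 0.9867 | 0.33876 |
| 1 | 0.3897 | 10 | 0.8981 | 0.35001 |
| 2 | 0.1966 | 12 | 0.6203 | 0.12196 |
| 3 | 0.0579 | 14 | 0.2402 | 0.01390 |
| 4 | 0.0110 | 16 | 0.0348 | 0.00038 |
| 5 | 0.0014 | 17 | 0.0073 | 0.00001 |
| 6 | 0.0001 | 18 | 0.0007 | <0.00001 |

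The sum is 0.8250. Rejections in the opposite direction add nothing visible. The power is 82.5%.

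**Step 3: where the difference arises.** Six tables with more events on active are significant by chi-square but not by Fisher. Together they carry 0.8541 − 0.8250 = 0.029 of probability under the alternative. Most of it (0.024) is one table, 9/18 versus 1/9: chi-square is 3.89, above 3.84, but Fisher p = 0.091. The planned analysis would call that result non-significant.

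**Step 4: other readings of the inputs.**

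| Reading | Power |
|---|---|
| Fisher two-sided, 2/3 versus 1/9 (if the rates are rounded fractions) | 82.1% |
| Fisher two-sided, 67.49% versus 11.15% (most favourable rounding) | 83.4% |
| Fisher one-sided at 5% | 82.8% |
| Fisher mid-p | 82.8% |
| Fisher two-sided by doubling the one-sided p | 73.5% |

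None reaches 85%.

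**Step 5: what the planned test can detect.** With control at 11.2%, two-sided Fisher power is 84.1% at an active rate of 68% and 85.6% at 69%. It crosses 85% at 68.6%. With the active rate held at 67%, the control rate would have to be about 9.9%.

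**The case against.** The 85% is not a calculation slip. It follows correctly from a common planning approximation, and section 2.3.3 does not claim that it was computed for Fisher's test. That stands: the fault is a mismatch between the power method and the planned test.

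The gap is also small. A control rate of 10% in place of 11.2% would bring Fisher power to 84.8%, so the discrepancy is about the size of a one-point change in an assumed rate. Section 2.3.3 already warns that only very large differences are detectable, and gives a second reason for the sample size: the chance of seeing at least one event. Enrolment is described in the past tense, so no decision on size remains open. All of this stands and limits the weight of the point.

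It can also be said that 68.6% literally satisfies a rate above 67%. That does not stand. If 67% is not the rate at which 85% is reached, the sentence states no detectable rate at all. The agreement of the approximation with 85% at exactly 67% indicates that 67% was meant as the threshold.

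Lastly, one might prefer the chi-square figure as it is. Its maximum true size with 18 and 9 participants is 6.3%, at a common event rate of about 27% or 73%, against 3.9% for Fisher. At the planned 11.2% rate its size is 4.3%, so this is a side remark. The SAP does not plan that test in any case.

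**Conclusion.** The point holds. At the SAP's own rates, arm sizes and level, the two-sided Fisher's exact test has 82.5% power, 2.5 points below the stated 85%. Its detectable rate at 85% power is 68.6% rather than 67%. The result assumes the usual definition of the two-sided Fisher p-value, rejection at p ≤ 0.05 and all 27 participants analysed. The sample size, planned test and interpretation of the trial are unaffected; the stated power should be corrected.

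**What to change.** Replace the power sentence in section 2.3.3 with wording to this effect: with a two-sided 5% Fisher's exact test and 18 versus 9 participants, the study has 82.5% power if the event rates are 67% and 11.2%, and at least 85% power if the active rate is about 69% or more against 11.2%.

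If the 85% is to be kept, the minimum is to say that it comes from an uncorrected normal approximation, and that the planned exact test has 82.5% at the same rates.

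The cost is one sentence and a slightly less favourable figure. No participants, data or analyses change.

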3. GENERAL DATA ANALYSIS CONSIDERATIONS

3.1 Analysis Set(s)

The analysis set for the primary safety endpoint will include all enrolled participants who received at least one dose of the study product (either the dapivirine or the placebo gel). The analysis set for the primary PK endpoint will include enrolled participants who were assigned to receive the active treatment and who received at least one dose of the study product (dapivirine gel).

Participants enrolled but lost to follow-up between enrollment visit (Visit 2) and the first dosing visit (Visit 3) or who were never administered the gel will not be included in the analysis sets. Enrolled participants who received the study product but were found to be ineligible (enrollment violations) will preferably be included in the analysis sets, in order to capture all adverse events potentially related to the study product. Sensitivity analysis of the primary safety endpoint excluding these participants will be conducted.

All the participants to be excluded from the analysis sets will be identified prior to data lock and to the unblinding of the data and the reasons for exclusion will be properly documented.

3.2 Statistical Analysis Issues

Based on previous MTN trials, minimal missing data is expected. Any missing data will be tabulated as a separate category when reporting data summaries.

If missing data rates are higher than anticipated (over 10%), sensitivity analyses for the primary safety endpoint will be conducted. For these sensitivity analyses, we will impute extreme values to the missing data and report the resulting analyses.

4. INTERIM ANALYSIS AND DATA MONITORING COMMITTEE

No interim statistical analysis was planned or performed for the MTN-026 study.

One safety monitoring committee (SMC) review was conducted for MTN-026, on May 14, 2018, for which a closed report was produced. Evaluation of safety was based on descriptive tables of adverse events, with no formal statistical testing.

5. GENERAL ANALYSIS METHODS

Descriptive statistics will be used to summarize continuous (mean and standard deviation, median and interquartile range, quartiles, range, and number of missing data values) and categorical (frequencies, relative frequencies, percentages, and number of missing data values) outcomes. Line, scatter, and box plots will be used, as appropriate, to visualize trends in longitudinally repeated measures.

Confidence intervals will be obtained using the Clopper-Pearson method for binary outcomes, while for continuous outcomes these will be based on the Student's-*t* statistic. Unless otherwise specified, 95% confidence intervals will be provided.

When use of formal testing to assess differences between participants in active and placebo arms are required, the following methods will be used: for binomial response variables, a Fisher's exact test; for continuous variables, t-tests or nonparametric methods. Unless otherwise specified, results from two-sided hypothesis tests will be reported.

6. TRIAL PARTICIPANT DISPOSITION

6.1 Disposition of Participants

Enrollment of participants took place at three study sites: Birmingham, AL, and Pittsburgh, PA, in the US and Bangkok in Thailand.

6.1.1 Study Screening and Enrollment

The number of participants screened, the number of participants who were enrolled and not enrolled, the number of participants with each reason for not enrolling, and the number of participants considered evaluable for each primary and secondary endpoint will be displayed in tables overall and by site. These summaries will also be displayed by arm in a CONSORT diagram.

Dates of site activation, first enrollment and last enrollment, as well as the number of participants enrolled the screening-to-enrollment ratio will be displayed in tables overall and by site and by arm.

6.1.2 Retention

For each visit, a participant is expected to have returned to the site clinic within a specified visit window, based on the participant's date of enrollment visit or, for sampling visits, based on the previous dosing visit. The proportion of participants retained at a scheduled visit is obtained by dividing the number of participants who have completed the visit by the number of participants expected for that visit. Tables will be presented that show by visit the number and percentage of expected, retained, missed visits, and lost-to-follow-up or terminated participants, overall and by arm and by site. No formal statistical testing will be conducted.

6.1.3 Treatment Discontinuation

The number and percentage of participants who ended product use early (prior to visit 13), as well as the reasons for terminating product use early, as collected on the Treatment Discontinuation electronic Case Report Form (eCRF), will be presented in tables by arm and by site. Reasons for ending study product use early include the following: acquisition of HIV infection, Adverse Event, reported use of prohibited medications, pregnancy, breastfeeding, anorectal STIs, participant unable/unwilling to comply with required study procedures or otherwise might be put at undue risk to their safety and well-being by

continuing product use according to judgment of IOR/designee, other. No formal statistical testing will be conducted.

6.1.4 Study Discontinuation

The number and percentage of the participants who completed the study, as well as the reasons for non-completion, as collected on the Study Discontinuation electronic Case Report Form (eCRF), will be presented in tables by arm and by site. Reasons for non-completion include the following: death, withdrawal of consent by participant, lost to follow-up, investigator decision, study terminated by sponsor, pregnancy, HIV infection, permanent study product discontinuation, other. No formal statistical testing will be conducted.

6.1.5 Visit Adherence: Completion of Procedures

Visit adherence will be summarized by completion of required and expected procedures overall and by site. This will be done for the following procedures (we mark with asterisk (*) those procedures that are expected only for female participants): 1) Physical exam; 2) vital signs; 3) sexual lubricant form; 4) pregnancy tests *; 5) chemistries; 6) pelvic exam *; 7) rectal exam; 8) plasma archive; 9) plasma for PK; 10) HIV Test; 11) CVL for PD*; 12) cervicovaginal fluid for PK *; 13) cervical tissue for PK *; 14) rectal fluid for PK; 15) rectal tissue for PK; 16) rectal fluid for mucosal safety; 17) rectal tissue for mucosal safety; 18) rectal tissue for PD; 19) rectal enema effluent for PK/PD; 20) behavioral assessment; 21) In-depth interview. Tables displaying the number and percentages of participant-visits for each of these categories by arm and site will be presented. No formal statistical testing will be conducted.

6.2 Treatment Exposure

Exposure to treatment, as collected on the Directly Observed Dosing Log eCRF at visit 3 and visits 7 to 13 will be described. The number and percentage of participants for whom the gel application was (i) observed in clinic, (ii) done in home, not observed or (iii) not done, will be displayed in tables by visit and site and by visit and study arm.

6.3 Protocol Deviations

A table with the number and type of protocol deviations will be presented, by site and by arm. A listing of all the protocol deviations will be presented, including the description of the deviations.

7. BASELINE DATA

7.1 Demographics

Demographics and baseline characteristics of participants as collected on the Demographics eCRF will be presented by arm and by site. These characteristics include age (continuous in years, and in categories of five years), sex at birth, gender identity, marital and cohabitation status, highest level of education, race, ethnicity, and income source. No formal statistical testing will be performed.

7.2 Baseline Medical History

A listing of all baseline medical history events as collected on the Baseline Medical History Log eCRF will be presented, including grade, severity/intensity, whether the condition is ongoing, and the beginning and end dates of the event. No formal statistical testing will be performed.

7.3 Vital Signs

Baseline vital signs as collected on the Vital Signs eCRF at Screening and Enrollment will be presented by arm and visit and by site and visit. Summary statistics appropriate for the measurement scale will be used to describe distribution of height (at Screening only), weight, body temperature, systolic blood pressure, diastolic blood pressure, pulse, and rate of respiration. No formal statistical testing will be performed.

7.4 Physical Exam

Baseline physical exam results as collected on the Physical Exam eCRF at Screening and Enrollment will be presented in tables by arm and visit and by site and visit. Number and percentage of participants experiencing any abnormal physical findings at each visit will be presented as well as the number and proportions of participants with findings for the following organ systems and body parts: general appearance; head, eye, ear, nose, and throat; oral mucosa; neck; lymph nodes; heart/cardiovascular; lung/respiratory; abdomen; extremities; neurological; skin; and other system. No formal statistical testing will be performed.

7.5 Anorectal and Pelvic Exams

Baseline results from the anorectal exam (all participants) and the pelvic exam (female participants only), as collected on the Anorectal Exam and Pelvic Exam eCRFs at Screening and Enrollment will be presented in tables by arm and visit and by site and visit. Number and percentage of participants experiencing any abnormal findings at each visit will be presented as well as the number and proportions of participants with specific types of anorectal or pelvic exam findings. No formal statistical testing will be performed.

7.6 Hematology

Baseline hemogram and differential results as collected on the Hematology eCRF at Screening will be presented in tables by arm and by site. Summary statistics appropriate for continuous variables will be used to describe each of the following: hemoglobin, hematocrit, MCV, platelets, WBC, neutrophils, lymphocytes, monocytes, eosinophils, and basophils. No formal statistical testing will be performed.

